## APPENDIX D THE WORLD HEALTH ORGANIZATION (WHO) CLASSIFICATION OF THE MYELODYSPLASTIC SYNDROMES (MDS)

Table 20: WHO classifications for MDS

WHO myeloid neoplasm and acute leukemia classification	Dysplastic findings	Cytopeniasa	PB and BM findings and cytogenetics
MDS with single lineage dysplasia	1	1 or 2	BM < 5%, PB < 1%, no Auer Rods
(MDS-SLD)			Any cytogenetics, unless fulfills all criteria for MDS with isolated del(5q)
MDS with multilineage dysplasia (MDS-	2 or 3	1-3	BM < 5%, PB < 1%, no Auer Rods
MLD)			Any cytogenetics, unless fulfills all criteria for MDS with isolated del(5q)
MDS with ring sideroblasts (MDS-RS) b			BM < 5%, PB < 1%, no Auer Rods
MDS-RS and single lineage dysplasia	1	1 or 2	Any cytogenetics, unless fulfills all
(MDS-RS-SLD)	2 or 3	1-3	criteria for MDS with isolated del(5q)
MDS-RS and multilineage dysplasia (MDS-RS-MLD)			
MDS with isolated del(5q)	1-3	1-2	BM < 5%, PB < 1%, no Auer Rods
			del(5q) alone or with 1 additional abnormality except -7 or del(7q)
MDS with excess blasts (MDS-EB)			
MDS-EB-1	0-3	1-3	BM 5-9% or PB 2-4%, no Auer Rods Any cytogenetics
MDS-EB-2	0-3	1-3	BM 10-19% or PB 5-19% or Auer Rods
			Any cytogenetics
MDS, unclassifiable (MDS-U)			
MDS-U with 1% blood blasts	1-3	1-3	BM < 5%, PB =1%c, no Auer Rods
			Any cytogenetics
MDS-U with SLD and pancytopenia	1	3	BM < 5%, PB <1%, no Auer Rods
			Any cytogenetics
MDS-U based on defining cytogenetic	0	1-3	BM < 5%, PB <1%, no Auer Rods
abnormality			MDS-defining abnormality d

Abbreviations: BM = bone marrow; del = deletion; FISH = fluorescence in situ hybridization; MDS = myelodysplastic syndromes; MDS-EB = MDS with excess blasts; MDS-EB-1 = MDS with excess blasts-1; MDS-EB-2 = MDS with excess blasts-2; MDS-MLD = MDS with multilineage dysplasia; MDS-RS = MDS with ring sideroblasts; MDS-RS-MLD = MDS-RS and multilineage dysplasia; MDS-RS-SLD = MDS-RS and single lineage dysplasia; MDS-SLD = MDS with single lineage dysplasia; MDS-U = MDS, unclassifiable; PB = peripheral blood; WHO = World Health Organization.

Protocol CA059-001 Amendment 3.0

930197534 2.0

Approved v2.0

<sup>a Cytopenias defined as: hemoglobin, <10 g/dL, platelet count, <100 x 10^9/L; and absolute neutrophil count, <1.8 x 10^9/L. Rarely, MDS may present with mild anemia or thrombocytopenia above these levels. Peripheral blood monocytes must be < 1 x 10^9/L.

b Cases with ≥ 15% ring sideroblasts by definition have significant erythroid dysplasia, and are classified as MDS-RS-SLD.

- c One percent PB blasts must be recorded on at least 2 separate occasions.
- d Abnormality must be demonstrated by conventional karyotyping, not by FISH or sequencing. The presence of +8, -Y, of del(20q) is not considered to be MDS-defining in the absence of diagnostic morphologic features of MDS. Sources: Arber, 2016 and Vardiman, 2009.

## APPENDIX E RESPONSE CRITERIA FOR MYELODYSPLASTIC SYNDROMES (MDS)

The revised recommendations of the International Working Group (IWG) for diagnosis, standardization of response criteria, treatment outcomes, and reporting standards for therapeutic trials in myelodysplastic syndromes (MDS) modified for this protocol.

Table 21: Modified IWG Response Criteria for MDS

Category	Response criteria (responses must last at least 4 weeks)			
Complete remission (CR)	Bone marrow: $\leq$ 5% myeloblasts with normal maturation of all cell lines a Persistent dysplasia will be noted a,b Peripheral blood c - Hemoglobin $\geq$ 11 g/dL  - Platelets $\geq$ 100 $\times$ 10  /L  - Neutrophils $\geq$ 1.0 $\times$ 10  /L b - Blasts 0%			
Morphologic CR with partial hematologic recovery (CRh)	Bone marrow: $\leq 5\%$ myeloblasts with normal maturation of all cell lines a Persistent dysplasia will be noted a,b Peripheral blood c - Hemoglobin $\geq 11$ g/dL  - Platelets $> 50 \times 10^9$ /L  - Neutrophils $> 0.5 \times 10^9$ /L b - Blasts $0\%$			
Partial remission (PR)	All CR criteria if abnormal before treatment, except:  Bone marrow blasts decreased by $\geq 50\%$ over pretreatment but still $> 5\%$ Cellularity and morphology not relevant			
Marrow CR b ± Hematologic Improvement (HI)	Bone marrow: ≤ 5% myeloblasts and decrease by ≥ 50% over pretreatment b Note: Blasts at baseline must be ≥ 5% in order for subject to be evaluable for Marrow CR d Peripheral blood: if HI responses, they will be noted in addition to marrow CR b			
Stable disease (SD)	Failure to achieve at least PR, but no evidence of progression for >			
Failure	Death during treatment or disease progression characterized by worsening of cytopenias, increase in percentage of bone marrow blasts, or progression to a more advanced MDS FAB subtype than pretreatment			
Relapse after CR or PR	At least 1 of the following:			
	
 
Return to pretreatment bone marrow blast percentage
 
Decrement of ≥50% from maximum remission/response levels in granulocytes or platelets
 
Reduction of Hgb concentration by ≥ 1.5 g/dL or transfusion dependence
 
			
Cytogenetic Response	Complete – Disappearance of the chromosomal abnormality without appearance of new ones  Partial – At least 50% reduction of the chromosomal abnormality			
Disease Progression (PD)	For subjects with:  • Less than 5% blasts: ≥ 50% increase in blasts to > 5% blasts  • 5% - 10% blasts: ≥ 50% increase in blasts to > 10% blasts  • 10% - 20% blasts: ≥ 50% increase in blasts to > 20% blasts  Any of the following:  • At least 50% decrement from maximum remission/response levels in granulocytes or platelets  • Reduction in Hgb concentration by ≥ 2 g/dL  • Transfusion dependence			

Table 21: Modified IWG Response Criteria for MDS

Category	Response criteria (responses must last at least 4 weeks)
Disease transformation	Transformation to AML (20% or more BM or PB blasts) d
Hematologic Improvement (HI)	
Erythroid response (HI-E)	Hgb increase by $\ge$ 1.5 g/dL
(Pretreatment < 11 g/dL)	Relevant reduction of units of RBC transfusions by an absolute number of at least 4 RBC transfusions. Compared with the pretreatment transfusion number in the previous only RBC transfusions given for a Hgb of $\leq 9.0$ g/dL pretreatment will count in the RBC transfusion evaluation
Platelet response (HI-P)	Absolute increase of $\geq 30 \times 10^9 / L$ for subjects starting with $> 20 \times 10^9 / L$
(Pretreatment $< 100 \times 10^{9}$ L)	Increase from $< 20 \times 10^9/L$ to $> 20 \times 10^9/L$ and by at least 100%
Neutrophil response (HI-N)	At least 100% increase and an absolute increase of $> 0.5 \times 10^9/L$
(Pretreatment $< 1.0 \times 10^9/L$ )	
Progression/relapse after HI	At least one of the following:
	At least 50% decrement from maximum response levels in granulocytes or platelets
	• Reduction in Hgb by ≥ 1.5 g/dL
	Transfusion dependence

Abbreviations: AML = acute myeloid leukemia; BM = bone marrow; CR = complete remission; FAB = French-American-British; Hgb = hemoglobin; HI = hematologic improvement; HI-E = HI - erythroid response; HI-P = HI - platelet response; HI-N = HI - neutrophil response; IWG = International Working Group; MDS = myelodysplastic syndromes; PB = peripheral blood; PD = Disease Progression; PR = partial remission; RBC = red blood cell; SD = stable disease.

- a Dysplastic changes should consider the normal range of dysplastic changes (modification).
- b Modification to IWG response criteria.
- In some circumstances, protocol therapy may require the initiation of further treatment (eg, consolidation, maintenance) before the 4-week period. Such subjects can be included in the response category into which they fit at the time the therapy is started. Transient cytopenias during repeated chemotherapy courses should not be considered as interrupting durability of response, as long as they recover to the improved counts of the previous course.
- d Sponsor modification of IWG criteria. Sources: Bloomfield, 2018; Cheson, 2006; Vardiman, 2009.

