#### 4.2 Inclusion Criteria

Subjects must satisfy the following criteria to be enrolled in the study:

- 1) Subject is  $\geq$  18 years of age, at the time of signing the ICF.
- 2) Subject must understand and voluntarily sign an ICF prior to any study-related assessments/procedures being conducted.

- 3) Subject is willing and able to adhere to the study visit schedule and other protocol requirements.
- 4) Parts A and B:
  - a. R/R AML: AML as defined by the 2016 WHO Classification (Appendix B) who have failed or who are ineligible for all available therapies for AML which may provide clinical benefit.
  - b. R/R MDS: MDS as defined by the 2016 WHO Classification (Appendix D) with intermediate, high or very high risk by IPSS-R (IPSS-R and who have failed or who are ineligible for all available therapies for MDS which may provide clinical benefit.
- 5) Part C: Treatment-naïve (ie, previously untreated) MDS as defined by the 2016 WHO Classification (Appendix D) with intermediate, high or very high risk by IPSS-R (IPSS-R . Prior administration of erythroid or myeloid growth factors and/or supportive transfusions is permitted unless otherwise specified (eg, in Section 4.3 and Section 8).
- 6) Part D: TN AML as defined by the 2016 WHO Classification (APPENDIX B), including secondary AML and therapy-related AML in subjects who are IE for IC and allogeneic due to having one of the following:
  - a. Severe cardiac comorbidities (including congestive heart failure, left ventricular ejection fraction [LVEF] <45%, and chronic stable angina).
  - b. Pulmonary comorbidity (diffuse capacity of the lung for carbon monoxide [DLCO]  $\leq$  65% or forced expiratory volume in 1 second [FEV1]  $\leq$  65%).
  - c. Any other comorbidity incompatible with intensive chemotherapy upon approval of the Sponsor Medical Monitor.
  - d. Aged  $\geq 75$  years, regardless of the presence of any of the above comorbidities.
    - i. Subjects must have a projected life expectancy of  $\geq 12$  weeks.
    - ii. TN AML subjects who have not received HMA, venetoclax, or chemotherapy in the setting of antecedent MDS are eligible. Prior treatment for MDS including, but not limited to growth factors (eg, erythropoiesis-stimulating g agents), hydroxyurea, and lenalidomide is allowed.
- 7) Eastern Cooperative Oncology Group Performance Status (ECOG PS) of 0 to 2.
- 8) Subjects must have the following laboratory values:

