# 9.6 Efficacy Analysis

The key efficacy variables are CRR (defined as CR + CRi + CRh for AML; CR for MDS) and ORR (all responses of CR [ie, CRMRD-, morphologic CR, CRh, CRi] + MLFS + PR for AML and CR + CRh + marrow CR + PR for MDS) by disease -appropriate response criteria. For dose expansion, efficacy variables to be analyzed include CRR and ORR, duration of remission, duration of response, stable disease rate (MDS only), relapse-free survival, event-free survival, progression-free survival, time to remission/response, transfusion independence, time to AML transformation for MDS subjects, and OS rates at 6 and 12 months. Point estimates and 2-sided 90% exact Clopper-Pearson confidence intervals of CRR and ORR will be reported. For time to event endpoints, Kaplan-Meier survival analyses will be performed. The PFS and overall survival rate will be measured and reported at pre-specified time points (ie, 6 months, 12 months).

Exploration of PK, PD, safety and activity relationships may be assessed.

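### The MDS CR and CRh rows of Table 21 carry no pretreatment condition, so a subject already inside the thresholds at screening can be counted as a responder while unchanged

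*Combined protocol and SAP*

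**What the plan says.** **Response rows (Appendix E, Table 21).** MDS CR needs marrow myeloblasts ≤5% with normal maturation in every lineage, hemoglobin ≥11 g/dL, platelets ≥100 × 10⁹/L, neutrophils ≥1.0 × 10⁹/L and no blood blasts. CRh is the same except that platelets need only exceed 50 and neutrophils 0.5. Both rows add "Persistent dysplasia will be noted". Responses must last at least 4 weeks. Neither row mentions values before treatment.

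The neighboring rows do:
- PR starts from "All CR criteria if abnormal before treatment" and needs blasts at least halved.
- Marrow CR needs baseline blasts ≥5% for the subject to be evaluable, and a fall of at least 50%.
- Hematologic improvement has pretreatment limits (hemoglobin <11, platelets <100, neutrophils <1.0).

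**Eligibility (Section 4.2).** Criterion 5 (Part C) reads "Treatment-naïve (ie, previously untreated) MDS as defined by the 2016 WHO Classification (Appendix D) with intermediate, high or very high risk by IPSS-R". Criterion 4b (Parts A and B) uses the same risk wording for relapsed/refractory MDS. The numeric IPSS-R cut-off is not visible. Appendix D, Table 20, footnote a lists "absolute neutrophil count, <1.8 x 10" (that is, × 10⁹/L) among the qualifying cytopenias, and several entities with marrow blasts below 5% need only one cytopenia.

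**Endpoints (Section 9.6).** MDS CRR is CR alone. ORR is "CR + CRh + marrow CR + PR for MDS". Both are reported with two-sided 90% exact intervals. Neither Section 6.4 nor Section 9.6 adds a baseline condition.

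**The concern.** A response should mean that the disease changed. IPSS-R can reach intermediate risk or worse almost entirely through karyotype, while CR and CRh are judged on blasts and counts. Someone can therefore be eligible on one set of features and already satisfy the response thresholds on the other. If that person simply stays the same for 4 weeks, the CR row can be read as met at the first assessment.

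CR at screening would feed both CRR and ORR; CRh at screening would feed ORR. Time to response would be shortened too. The cohorts have no control arm in which the same artifact would appear, and the Safety Review Committee uses preliminary efficacy, together with safety, PK and PD, when it selects dose.

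**Working it through.** The plan gives no figure to reproduce. The check is whether an eligible subject can sit inside the thresholds at screening.

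**Inputs (Appendix G, Tables 24 and 25).** Cytogenetics: very good 0, good 1, intermediate 2, poor 3, very poor 4. Marrow blasts: ≤2% 0, >2 to <5% 1, 5–10% 2. Hemoglobin ≥10: 0. Platelets ≥100: 0; 50 to <100: 0.5. ANC ≥0.8: 0; <0.8: 0.5. Risk: intermediate >3 to 4.5, high >4.5 to 6, very high >6.

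**Step 1: CR thresholds at screening.** With hemoglobin ≥11, platelets ≥100 and ANC 1.0 to <1.8 (the WHO cytopenia), all counts score 0, so IPSS-R = cytogenetics + blasts.
- Very poor karyotype, blasts 3%, hemoglobin 11.5, platelets 120, ANC 1.5: 4 + 1 + 0 + 0 + 0 = 5.0, High.
- The text admits the intermediate category, which ends at 4.5, so 5.0 passes any hidden cut-off consistent with that wording.

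**Step 2: CRh thresholds at screening.** The same subject with platelets 70: 4 + 1 + 0 + 0.5 + 0 = 5.5, High. A lower-risk case is poor karyotype, blasts 2%, platelets 70: 3 + 0 + 0 + 0.5 + 0 = 3.5, Intermediate. This one is eligible only if the hidden cut-off allows it.

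**Step 3: all score combinations above 3** (cytogenetic group × blast band × total count points).

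| Category met at screening | Combinations | Needing blasts of exactly 5% | Remaining | Highest remaining score |
|---|---|---|---|---|
| CR (count points 0) | 6 | 3 | 3 | 4 + 1 = 5 |
| CRh (count points 0, 0.5 or 1.0) | 6 + 9 + 9 = 24 | 3 + 4 + 4 = 11 | 13 | 4 + 1 + 1 = 6 |

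These show that the overlap exists. They say nothing about how often it occurs.

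**Step 4: the maturation requirement.** If it is read strictly, a dysplastic subject fails CR and CRh. Table 20 still admits two entities with 0 dysplastic lineages:
- MDS-U by defining cytogenetic abnormality, with marrow blasts <5%.
- MDS-EB-1, where blasts of exactly 5% satisfy both entry and the ≤5% rule. With CR-level counts the score is 2 + 2 = 4, 3 + 2 = 5 or 4 + 2 = 6 for intermediate, poor or very poor cytogenetics.

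**Step 5: consistency within Table 21.** One sufficient criterion for relapse after CR is a marrow blast percentage back at its pretreatment level. A subject unchanged since screening would meet CR and that relapse criterion together, which also confuses duration of remission.

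**Step 6: size per case.** Each such subject adds 1/n. Cohort sizes are blacked out, so n = 20, 30 and 40 are assumptions, as are 20% genuine CRs and two subjects already meeting CR.

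| n | Genuine CRs only (90% CI) | Two unchanged subjects added (90% CI) | 1/n |
|---|---|---|---|
| 20 | 4/20 = 20.0% (7.1–40.1) | 6/20 = 30.0% (14.0–50.8) | 5.0 points |
| 30 | 6/30 = 20.0% (9.1–35.7) | 8/30 = 26.7% (14.0–43.0) | 3.3 points |
| 40 | 8/40 = 20.0% (10.4–33.2) | 10/40 = 25.0% (14.2–38.7) | 2.5 points |

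**The case against.** **Maturation.** Most Table 20 entities with blasts below 5% require at least one dysplastic lineage, and footnote a of Table 21 can be read as tolerating only dysplasia within the normal range. On that reading the gap narrows to the two entities in Step 4. This stands as a limit on size, but the row's own wording on persistent dysplasia supports the looser reading equally well, and the strict reading does not close the gap.

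**Table 21 presupposes change.** The relapse criterion and the phrase response to treatment both imply it. That is fair evidence of intent. It does not supply a rule, and the rows beside CR and CRh show that the plan writes the condition out where it wants one.

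**Hidden text.** The IPSS-R cut-off, many exclusions in Section 4.3, the Efficacy Evaluable definition in Table 13 and the Table 3 efficacy footnote cannot be read. A baseline or evaluability condition could be there. This stands and lowers confidence in how many subjects are affected.

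**Consequence.** Safety and the RP2D are primary, CRR and ORR are secondary, and all analyses are descriptive. This also stands; the point concerns the accuracy of two key efficacy rates.

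**Remedy.** Requiring one unmet threshold does not guarantee a meaningful change: ANC moving from 0.99 to 1.01 could still complete a CR. That is true of any threshold rule.

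**Conclusion.** On the readable text the gap is real. The MDS CR and CRh rows lack a pretreatment condition that their neighbors have, and the visible eligibility text admits subjects who already meet all the blast and count thresholds. Such a subject, unchanged for 4 weeks, can be counted in CRR and ORR (CR) or in ORR alone (CRh).

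The size is 1/n per case. Frequency is unknown and probably low. For CR it needs hemoglobin ≥11, platelets ≥100, isolated mild neutropenia and, below 5% blasts, poor or very poor cytogenetics. CRh is broader but still needs hemoglobin ≥11.

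Two stronger readings are tempting:
- A reader might infer that the MDS rates will be inflated by some predictable number of points. The documents give no share of subjects inside the thresholds at entry and no visible cohort size, so no overall inflation can be stated.
- A reader might infer that the overlap extends through the very high risk group. Scores above 5 for CR or 6 for CRh depend wholly on blasts of exactly 5%.

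The conclusion assumes that no blacked-out eligibility or evaluability text imposes a baseline condition.

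**What to change.** 1. Add to the CR and CRh rows of Table 21 that the category counts as a response only if at least one of its own blast or count thresholds was not met at screening. A subject who meets CRh but not CR at screening can then still score CR.
2. Report, for each MDS cohort, how many subjects already met CR or CRh at screening.
3. Give CRR and ORR with these subjects not evaluable for the category concerned, following the marrow CR row, and as a sensitivity analysis with them as non-responders. In the n = 20 illustration these give 4/18 = 22.2% and 4/20 = 20.0%, against 6/20 = 30.0% under the current wording.

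The cost is one line in Table 21 and one derivation rule, using the marrow and blood count data already collected at screening (Section 6.1). MDS CRR and ORR may read slightly lower. The non-responder version is conservative, because it keeps in the denominator subjects who cannot score that category.

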## APPENDIX F RISK STATUS BASED ON CYTOGENETICS FOR ACUTE MYELOID LEUKEMIA

Table 22: Risk Stratification by Genetics in Non-APL AML

Risk Category*	Genetic Abnormality
Favorable	t(8;21)(q22;q22.1); RUNX1-RUNX1T1
	inv(16)(p13.1q22) or t(16;16)(p13.1;q22); CBFB-MYH11
	Biallelic mutated CEBPA
	Mutated NPM1 without FLT3-ITD or with FLT3-ITD low †
Intermediate	Mutated NPM1 and FLT3-ITD high †
	Wild-type NPM1 without FLT3-ITD or with FLT3-ITD low † (without adverse-risk genetic lesions)
	t(9;11)(p21.3;q23.3); MLLT3-KMT2A‡
	Cytogenetic abnormalities not classified as favorable or adverse
Poor/Adverse	t(6;9)(p23;q34.1); DEK-NUP214
	t(v;11q23.3); KMT2A rearranged
	t(9;22)(q34.1;q11.2); BCR-ABL1
	inv(3)(q21.3q26.32) or t(3;3)(q21.3;q26.2); GATA2,MECOM(EV11)
	-5 or del(5q); -7; -17/abn(17p)
	Complex karyotype§, monosomal karyotype
	Wild-type NPM1 and FLT3-ITD high †
	Mutated RUNX1¶
	Mutated ASXL1¶
	Mutated TP53#

Abbreviations: ABL1 = ABL proto-oncogene 1; abn = arm band number; ASXL1 = ASXL transcriptional regulator 1; BCR = breakpoint cluster region protein; CBFB = core-binding factor subunit  $\beta$ ; CEBPA = CCAAT/enhancer binding protein  $\alpha$ ; DEK = DEK proto-oncogene; del = deletion; FLT3-ITD = FLT3 internal tandem duplication; GATA2 = GATA binding protein 2; KMT2A = lysine methyltransferase 2A; inv = inversion; MECOM(EV11) = MDS1 and EV11 complex locus protein (ecotropic virus integration site 1 protein homolog); MLLT3 = myeloid/lymphoid or mixed-lineage leukemia (trithorax homolog, Drosophila), translocated to, 3; MYH11 = myosin heavy chain 11; NPM1 = nucleophosmin 1; NUP214 = nucleoporin 214; p = short arm of a chromosome; q = long arm of a chromosome; RUNX1 = runt-related transcription factor 1; RUNX1T1 = RUNX1 partner transcriptional corepressor 1; t = translocation; TP53 = tumor protein 53.

- \* Prognostic impact of a marker is treatment-dependent and may change with new therapies.
- † Low, low allelic ratio (<0.5); high, high allelic ratio (≥0.5); semiquantitative assessment of FLT3-ITD allelic ratio (using DNA fragment analysis) is determined as ratio of the area under the curve "FLT3-ITD" divided by area under the curve "FLT3-wild type"; recent studies indicate that AML with NPM1 mutation and FLT3-ITD low allelic ratio may also have a more favorable prognosis and patients should not routinely be assigned to allogeneic HCT. FLT3 allelic ratio is not yet pervasively used, and IF not available, the presence of an FLT3 mutation should be considered high-risk unless it occurs concurrently with an NPM1 mutation, in which case it is intermediate risk. As data emerge, this measure will evolve.
- ‡ The presence of t(9;11)(p21.3;q23.3) takes precedence over rare, concurrent adverse-risk gene mutations.
- § Three or more unrelated chromosome abnormalities in the absence of 1 of the WHO-designated recurring translocations or inversions, that is, t(8;21), inv(16) or t(16;16), t(9;11), t(v;11)(v;q23.3), t(6;9), inv(3) or t(3;3); AML with BCR-ABL1.
- Defined by the presence of 1 single monosomy (excluding loss of X or Y) in association with at least 1 additional monosomy or structural chromosome abnormality (excluding core-binding factor AML).

¶ These markers should not be used as an adverse prognostic marker if they co-occur with favorable-risk AML subtypes.

# TP53 mutations are significantly associated with AML with complex and monosomal karyotype.

Source: NCCN, 2021a.

### APPENDIX G FOR MDS

### REVISED INTERNATIONAL PROGNOSTIC SCORING SYSTEM

Table 23: IPSS-R Cytogenetic Risk Groups

Cytogenetic Prognostic Subgroups	Cytogenetic Abnormalities	
Very good	-Y, del(11q)	
Good	Normal, del(5q), del(12p), del(20q), double including del(5q)	
Intermediate	del(7q), +8, +19, i(17q), any other single or double independent clones	
Poor	-7, inv(3)/t(3q)/del(3q), double including -7/del(7q), Complex: 3 abnormalities	
Very poor	Complex: > 3 abnormalities	

Abbreviations: del = deletion; inv = inversion; IPSS-R = Revised International Prognostic Scoring System score; p = short arm of a chromosome; q = long arm of a chromosome; t = translocation.

Source: Greenberg, 2012.

Table 24: IPSS-R Prognostic Score Values

Prognostic variable	0	0.5	1	1.5	2	3	4
Cytogenetics	Very Good	-	Good	-	Inter- mediate	Poor	Very Poor
Bone Marrow Blast (%)	≤ 2	-	> 2 - < 5	-	5 - 10	> 10	-
Hemoglobin (g/dL)	≥10	-	8 - < 10	<8	-	-	-
Platelets (× 10  /L)	≥100	50 - < 100	< 50	-	-	-	-
ANC (× 10  /L)	≥0.8	< 0.8	-	-	-	-	-

Abbreviations: ANC = absolute neutrophil count; IPSS-R = Revised International Prognostic Scoring System score. Source: Greenberg, 2012.

The total IPSS-R score is calculated as the sum of the cytogenetics, bone marrow blast percentage, hemoglobin, platelets, and ANC individual scores.

Table 25: IPSS-R Prognostic Risk Categories/Scores

Risk Category	Risk Score
Very Low	≤1.5
Low	> 1.5 – 3
Intermediate	> 3 – 4.5
High	> 4.5 - 6
Very High	> 6

Abbreviations: IPSS-R = Revised International Prognostic Scoring System score.

Source: Greenberg, 2012.

Protocol CA059-001 Amendment 3.0

Table 26: IPSS-R: Prognostic Risk Category Clinical Outcomes

Prognostic variable	No. pts	Very Low	Low	Intermediate	High	Very High
Subjects, %	7012	19%	38%	20%	13%	10%
Median Overall Survival (years)	-	8.8	5.3	3.0	1.6	0.8
Median time to 25% AML evolution	-	Not reached	10.8	3.2	1.4	0.73

Abbreviations: AML = acute myeloid leukemia; IPSS-R = Revised International Prognostic Scoring System score. Source: Greenberg, 2012.

